**Statistical Analyses**

Statistical analyses of any differences between the 2 groups were performed using SPSS version 22 (SPSS Inc. Chicago, IL). Data were presented as means  $\pm$  standard deviations or as medians and interquartile ranges where appropriate. For dichotomous outcomes, treatment groups were compared by means of the  $\chi^2$  test. The Mann–Whitney U test and Kruskal–Wallis tests were used for continuous, not normally distributed outcomes. For continuous normally distributed data, the ANOVA test was used.

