Lymphadenectomy has different objectives: staging the tumor in the surgical act and trying to perform a complete resection to improve oncological results, this way evaluating the quality of the surgical procedure. There is a direct correlation between the number of lymph nodes excised, and therefore evaluated, with survival. For a long time is known that the existence of ganglia in the surgical piece depends on the surgical technique and the methodology used. The Clinical Guidelines recommend a minimum of 12 lymph nodes studied for a correct tumor stage. For years, minimally invasive surgery is performed in a large number of interventions in a safe way. Jacobs et al described the first laparoscopic resection in sigma cancer in 1991. Since then the experience has grown rapidly, and different clinical trials showed improvements in the postoperative period of the patient without oncological differences. Only the Lacy study showed greater lymph node excision with the laparoscopic technique.

At present laparoscopic surgery has show to be a safe technique, which a better recovery of the patient (decreasing postoperative ileus, early oral diet, more controlled pain, fewer days of hospital stay ...) and also reduces the rates of complications if performed by experienced surgical teams. The most recent randomized studies have shown no oncological differences with respect to open surgery. The percentage of conversion in the literature varies from 2 to 46% depending mainly on the experience of the team.

Among surgical techniques by means of minimally invasive surgery, right colectomy can be considered a particular case in which the technical difficulty added by the frequent anatomical variations, especially vascular ones, have meant a more gradual acceptance of the laparoscopic approach. Unlike the technique used in rectal-sigmoid neoplasms, ileocolic anastomoses after right hemicolectomy can be performed in two ways: extracorporeal or intracorporeal.

The extracorporeal anastomosis is performed by externalizing the ileum and colon through the incision through which the surgical specimen is extracted. The intracorporeal anastomosis is performed completely laparoscopically, and the incision made is only to remove the surgical specimen.

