## **MATERIALS AND METHODS:**

Patients treated in 4 Spanish South-east hospitals with preoperative diagnosis of right colon neoplasm were included. All participating hospitals have vast experience in minimally invasive approach.

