### **Study Design**

The IVEA-study is a prospective multicenter randomized trial with two parallel groups being done IA or EA in laparoscopic right hemicolectomy for right colon neoplasia. The patients were randomized using <http://www.randomization.com>.

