### **Outcome Measures**

Patient baseline characteristics at the time of surgery; age, gender, ASA score, major comorbidities and operative variables were obtained from each patient. The 30-day postoperative complications were recorded. Complications were defined as any deviation from the normal postoperative course and graded using Clavien-Dindo classification. The term anastomotic leakage (AL) defines all conditions with clinical or radiologic anastomotic dehiscence, with or without the need of surgical revision. Wound infection was defined as spontaneous drainage of purulent material from the wound or from the surgeon's deliberate revision and a positive culture of drained serous fluid. The length of hospital stay (LOS), reinterventions, postoperative pain according to the visual analogical scale were also documented. For the subsequent analysis of the patient, the conversion to an extracorporeal anastomosis among the totally laparoscopic procedures or conversion to open surgery has not been included.

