**Sample Size Calculation**

The hypothesis of this trial is that IRA will reduce overall postoperative 30-day morbidity rate. The sample size calculation is based on the detection of significant difference in the primary endpoint parameter of the trial. We assumed a postoperative complication rate of 30% in ERA according with several complication rates after colorectal surgery. With an expected complication rate of 11% in IRA, the sample size necessary for the trial with a power of 80% and one-sided significance level of 0.05 was calculated to be 75 patients per group. An assumed 10% drop-out rate in this trial will raise the sample size to 84 patients per group. Therefore, at least a total of 168 patients have to be included to the trial.

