### **CHRONOGRAM-PHASES OF WORK:**

- **SURGICAL INTERVENTION:** We will perform surgical interventions throughout the first 18 months of the study. Patients will be randomized and, depending on the group, the technique will be performed by intra-or extracorporeal anastomosis. During the first eighteen months.
- **FOLLOW UP:** Patients will be assessed daily during their hospital stay, and subsequently in consultation according to the protocol that is attached in methodology.
- **DATA COLLECTION:** All data will be included in the data collection notebook, and will be added in a Microsoft Access XP database, throughout the entire study.
- **STATISTICAL STUDY:** Once all the data have been collected, a statistical study will be carried out using the SPSS program as described in the data analysis (methodology). One month
- **REDACTION OF RESULTS.** The results will be written when the definitive statistical study is carried out according to: introduction, objectives, hypothesis, patients and methods, results, discussion, conclusions and bibliography. Five months.

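### Should the binary primary endpoint be adjusted for hospital and ASA score rather than tested with a plain chi-square?

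*Protocol*

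**What the plan says.** The Sample Size Calculation section sets the primary hypothesis: "The hypothesis of this trial is that IRA will reduce overall postoperative 30-day morbidity rate". The endpoint is binary, planned at 30% against 11% with "power of 80% and one-sided significance level of 0.05" and 75 patients per group before drop-out.

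For the analysis, the Statistical Analyses section states: "For dichotomous outcomes, treatment groups were compared by means of the" chi-square test. It names no covariate, stratum or centre term. The Chronogram section refers back to this text: "a statistical study will be carried out using the SPSS program as described in the data analysis (methodology").

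The candidate covariates appear elsewhere. Materials and Methods opens with "Patients treated in 4 Spanish South-east hospitals", and Outcome Measures says that "age, gender, ASA score, major comorbidities and operative variables were obtained from each patient". On allocation, Study Design says "The patients were randomized using" a named website and mentions neither strata nor blocks.

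**The concern.** Adjusting a binary endpoint for strong baseline predictors usually adds some precision and guards the estimate against chance imbalance. Here the ingredients seem to be at hand. ASA score is collected, hospital must be known in a multicentre trial, and since no stratification is described, the analysis is the only described place where an imbalance could be corrected. The Background even links outcome to the operating team, saying that laparoscopy "also reduces the rates of complications if performed by experienced surgical teams". If hospital and ASA do predict complications, a crude comparison leaves precision unused, and an unlucky allocation shifts the estimated risk difference. Changing the analysis wording would need no extra patients or data.

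**Working it through.** **Inputs.** From the Sample Size Calculation section: 30% vs 11%, one-sided 0.05, 75 per group. The protocol gives no prognostic strength for ASA or hospital and no share of high-ASA patients. Those below are assumptions: 40% high ASA, and ASA odds ratios from 1 to 4.

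**The plan's own figure.** With pooled variance under the null, √(2 × 0.205 × 0.795) = 0.571 and √(0.30 × 0.70 + 0.11 × 0.89) = √0.3079 = 0.555.

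- One-sided: n = [(1.645 × 0.571 + 0.842 × 0.555) / 0.19]² = 54.8, so 55 per group.
- Two-sided: the same formula with 1.960 gives 69.7, so 70 per group.

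The stated 75 is not reproduced. That is a separate matter, and it does not favour adjustment, since 75 exceeds both results. The drop-out step does reproduce: 75 / 0.90 = 83.3, so 84 per group and 168 in total.

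**Power of the chi-square at 75 per group.** Φ[(0.19 × √75 − 1.645 × 0.571) / 0.555] = Φ(1.273) = 0.898 one-sided. With 1.960 it is Φ(0.949) = 0.829 two-sided.

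**Validity.** In 4,000 simulated trials per setting, the chi-square's type I error was 0.048 to 0.056 one-sided and 0.045 to 0.052 two-sided, from no prognostic effect up to an ASA odds ratio of 4 with a hospital log-odds SD of 0.7.

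**How much there is to gain from ASA.** Take an odds ratio of 2 and 40% high ASA.

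- A 30% overall rate splits into 24.1% (low ASA) and 38.8% (high ASA), a gap of 14.7 points.
- An 11% rate splits into 8.2% and 15.2%, a gap of 7.0 points.
- The share of the risk difference's variance due to ASA is 0.40 × 0.60 × (0.147² + 0.070²) / 0.3079 = 2.1%.
- Removing all of it would cut the SD by 1 − √(1 − 0.021) = 1.0%.

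Against this stands the cost of estimating four extra terms (three for hospital, one for ASA). With no prognostic effect, simulation put that cost at 1.5% on the SD. Gain and cost are of the same size.

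**Simulated one-sided power, 75 per arm.** The adjusted test is a logistic model on arm, hospital and ASA, giving a standardised risk difference with an HC3-type standard error. Two separate simulations of this test were run; the first used 20,000 trials per setting. Its weak setting has ASA odds ratio 2.0 and hospital log-odds ±0.2, ±0.5; its strong setting has 2.5 and ±0.3, ±0.7.

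| Assumed prognostic effect | Simulation 1: crude → adjusted | Simulation 2: crude → adjusted |
|---|---|---|
| None | 90.7 → 89.8 | 90.9 → 89.8 |
| Weak | 90.6 → 90.5 | 91.3 → 90.7 |
| Strong | 90.6 → 91.5 | 90.8 → 90.8 |
| ASA odds ratio 4 | not run | 90.4 → 91.6 |

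The change runs from −1.1 to +1.2 points, and only the strongest setting of each simulation shows a gain or no loss. A likelihood-ratio test from the adjusted logistic model did somewhat better, from no gain to about 2.5 points. However, its type I error ran at 0.050 to 0.062 one-sided, so part of that gain is inflation.

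**Chance imbalance.** The SD of the difference in high-ASA share between arms is √(2 × 0.40 × 0.60 / 75) = 0.08. A gap of 10 points or more therefore has probability 2 × Φ(−0.10 / 0.08) = 2 × Φ(−1.25) = 21%. Such gaps average 14 points. Split evenly between arms at an odds ratio of 2, that moves the crude risk difference by 0.07 × (14.7 + 7.0) = 1.5 points. Simulation gave 1.5 to 1.6 points at odds ratio 2 and 1.7 to 1.9 at 2.5.

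The standard error of the risk difference is √(0.3079 / 75) = 6.4 points. The shift is therefore 1.5 / 6.4 = 0.23 to 1.9 / 6.4 = 0.30 of a standard error. It is one component of the random variation that the standard error already measures, not a bias added to it.

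**The case for a change.** The strongest counter-argument is that the protocol does more than leave this to a statistical analysis plan: it names the test, and the Chronogram refers back to it. Only one trial will be run, and about one in five allocations would carry an ASA gap of 10 points or more. With a single unstratified list of 84 and 84, the chance that some hospital's arms differ by 10 or more patients is about 33% if each hospital recruits 42, and 29% if they recruit 70, 50, 30 and 18 (both assumed). In the ASA case, adjustment cuts the shift to 0.2 points or less.

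The facts in this stand, and so does the conditional benefit. What does not follow is that the named test is a bad choice.

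- Averaged over allocations, the replacement performs about the same.
- The hospital figures show unequal numbers, not a shift in the estimate, and Study Design does not say whether there was one list or several.
- The Background remark concerns experienced teams in general, and Materials and Methods describes all four hospitals as highly experienced. No section says that ASA predicts complications here.
- The remedy has its own costs. About 0.30 × 75 + 0.11 × 75 = 31 events would support five terms besides the intercept, roughly six events per term. Without a small-sample correction, the standardised test's type I error was 5.3% to 6.0%.

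**Conclusion.** The concern does not hold. The unadjusted chi-square is a valid primary test for this design, and the protocol neither contradicts itself nor misstates anything in choosing it. Replacing it with a model adjusted for hospital and ASA changes one-sided power by about 1 point in either direction, around a base of roughly 90% at 75 per arm. In the 20,000-trial simulation the SD of the risk difference moved by +1.5% to −1.8%. The shift from a sizeable ASA imbalance is at most about 0.3 of a standard error and already lies within the test's error rate.

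This rests on the planned rates of 30% and 11%, on an assumed 40% of high-ASA patients, and on ASA odds ratios up to 4. Much stronger predictors would tilt the balance towards adjustment, but the protocol gives no reason to expect them. Adjusting remains a reasonable option on which statisticians differ. It is commonly settled in a statistical analysis plan, which is not at hand for this trial.

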### **Insurance policy**

An insurance policy will not be subscribed given that it is not a clinical trial with medications, and that the following conditions are met:

1. The surgical treatments that are applied in the trial are authorized in Spain and their use is adjusted to the conditions authorized and of usual practice. 2. The interventions to which the subjects will be submitted for their participation in the trial suppose a risk equivalent or inferior to the one that would correspond to their attention in the usual clinical practice; complying with the criteria of clinical trial of low level of intervention as specified by Royal Decree 1090/2015, of December 4 that regulates clinical trials with drugs, the Research Ethics Committees with medicines and the Spanish Registry of Clinical Studies.

### **CHRONOGRAM-PHASES OF WORK:**

- **SURGICAL INTERVENTION:** We will perform surgical interventions throughout the first 18 months of the study. Patients will be randomized and, depending on the group, the technique will be performed by intra-or extracorporeal anastomosis. During the first eighteen months.
- **FOLLOW UP:** Patients will be assessed daily during their hospital stay, and subsequently in consultation according to the protocol that is attached in methodology.
- **DATA COLLECTION:** All data will be included in the data collection notebook, and will be added in a Microsoft Access XP database, throughout the entire study.
- **STATISTICAL STUDY:** Once all the data have been collected, a statistical study will be carried out using the SPSS program as described in the data analysis (methodology). One month
- **REDACTION OF RESULTS.** The results will be written when the definitive statistical study is carried out according to: introduction, objectives, hypothesis, patients and methods, results, discussion, conclusions and bibliography. Five months.

### **AVAILABLE MEDIA: MATERIAL (PROVIDED BY THE OWN CENTER):**

There is adequate surgical space with all the necessary material for the realization of both interventions: Operating room; two laparoscopic towers (camera source, light source, CO2 insufflator, monitors), laparoscopic optics of 0° and 30°; optics and last generation laparoscopy tower; laparoscopy box for colorectal surgery (complete equipment of laparoscopic instruments); hemostasis and cutting device (Ligasure®, Ultracision®) ...  
In addition, a computer system is available in an intrahospital network so that the database of the coloproctology unit can be consulted from different teams.

